## 8.2 Statistical Analysis Plan

Target sample size is 12 participants, which was chosen as a feasible number that could be accrued within a 2 year accrual period. Participants will be randomized 1:1 to treatment arms A and B with block randomization using blocks of size 2 or 4. Participants are considered evaluable if they satisfy all inclusion and exclusion criteria and have adequate endpoint measurements during respective cohort timelines. Adjusting for a 10% unevaluable/drop-out rate, maximum target accrual is estimated at 15 participants.

The purpose is to assess the adverse events profile of pembrolizumab and focused ultrasound therapy and estimate the difference in the TILs at baseline and 3 weeks within each arm, not to make definitive comparisons between arms. With 6 participants per arm, there is limited power to make comparisons between arms. Lu et. al. (2009) data estimates the difference in means of the ratio of CD4+ and CD8+ cells for patients treated with HIFU versus no HIFU to be 0.57, with standard deviations ranging from 0.27 to 0.40. These data provide an indication of the magnitude that could be detected in this study at baseline and 3 weeks, where it is assumed that the no HIFU participants in Lu et. al. are comparable to baseline measurements in our study. Using these data as a guideline, with n=6, we have 80% power to detect an effect size of 1.44 for the within-arm change in ratio of CD4+ and CD8+ cells at baseline and 3 weeks. Depending on the variability of the data, this is equivalent to detecting differences of 0.39 and 0.58, for assumed standard deviations of 0.27 and 0.40, respectively. The populations will include all intention to treat participants.

Safety stopping rules will be employed within each arm and will be judged by dose limiting toxicities (DLT). If the first two participants within an arm or 3 out of the 6 participants within an arm experience a DLT, that arm will be deemed too toxic and further accrual to that arm will be closed. This decision rule is based on Wald's sequential probability ratio test assuming lower and upper DLT proportions of 0.1 and 0.3, respectively, and type I and II error rates of 10%.

Adverse events and DLTs will be summarized by frequency and magnitude for each arm and overall. Change in the proportion of CD8+ to CD4+ tumor infiltrating lymphocytes (TILs) in the primary ablation zone will be estimated by arm. Additionally change in CD8+ T-cell responses at peri-ablation zones and clinical response at local and distant metastatic sites measured by abscopal tumor shrinkage at non-ablated sites, will be estimated for each arm. The Kaplan Meier estimator will be used to estimate survival curves for DFS and OS. Exploratory endpoints including change in T-cells in peripheral blood, markers of T-cell activation, gene expression profiling, and enumeration of myeloid derived suppressor cells will be estimated by arm.

If highly favorable responses are seen in this pilot patient population, then this study may be expanded by means of an amendment to more rigorously define response criteria in either or both arms.

**Product:** Pembrolizumab

**Protocol/Amendment No.:** UVA Breast 48

V04-13-21

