## 1.0 TRIAL SUMMARY

Abbreviated Title	Focused Ultrasound combined with Pembrolizumab in Metastatic Breast Cancer
Trial Phase	Pilot
Clinical Indication	Metastatic Breast Cancer
Trial Type	Investigator Initiated
Type of control	N/A
Route of administration	IV
Trial Blinding	N/A
Treatment Groups	Arm A: Pembrolizumab after High-Intensity Focused Ultrasound (HIFU) Arm B: Pembrolizumab before High-Intensity Focused Ultrasound (HIFU)
Number of trial subjects	Up to 15
Estimated enrollment period	2 years
Estimated duration of trial	3 years
Duration of Participation	90 days to 2 years
Estimated average length of treatment per patient	90 days

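### The DLT stopping rule in Section 8.2 ends at six participants per arm, while the accrual ceiling of 15 puts seven or eight in an arm

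*Combined protocol and SAP*

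**What the plan says.** All the figures are in Section 8.2 unless another section is named.

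- **Target:** "Target sample size is 12 participants, which was chosen as a feasible number that could be accrued within a 2 year accrual period". The power discussion takes six per arm: "With 6 participants per arm, there is limited power to make comparisons between arms".
- **Allocation:** "Participants will be randomized 1:1 to treatment arms A and B with block randomization using blocks of size 2 or 4".
- **Ceiling:** "Adjusting for a 10% unevaluable/drop-out rate, maximum target accrual is estimated at 15 participants". The Trial Summary (Section 1.0) agrees: "Number of trial subjects Up to 15".
- **Evaluability:** "Participants are considered evaluable if they satisfy all inclusion and exclusion criteria and have adequate endpoint measurements during respective cohort timelines".
- **Stopping rule:** "If the first two participants within an arm or 3 out of the 6 participants within an arm experience a DLT", the arm is judged too toxic and takes no further participants. The rule is attributed to Wald's sequential probability ratio test (SPRT) with DLT proportions of 0.1 and 0.3 and error rates of 10% each.
- **Replacement (Section 5.9.1):** a participant may be replaced only if they received no study drug and no study procedure.

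Section 8.2 gives no threshold for a seventh or eighth participant. It does not say which participants make up the six.

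**The concern.** The accrual ceiling and the safety rule sit in the same section and do not fit each other. The ceiling lets each arm pass six, and the rule has nothing to say there. Suppose an arm has two DLTs among its first six and the seventh participant has a third. The rule as written neither closes the arm nor calls it too toxic, although the test it is said to rest on would.

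Section 4.4 describes this as the first study to combine the two treatments in humans. Section 10.7 asks the monitoring committee to review how the stopping rules are applied, and beyond six it has no stated rule to apply. The undefined denominator adds to the problem. A participant can be treated, lack a usable biopsy and so be unevaluable for the immune endpoint, and still be at risk of a DLT.

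**Working it through.** **1. How many participants an arm can reach.** With blocks of 2 or 4, the 15th participant is either the first place of a new block after 14 balanced places, or the third place of a block of four after 12 balanced places. Both give 8/7.

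**2. Reproducing the plan's rule.** The SPRT inputs are p0 = 0.1, p1 = 0.3 and α = β = 0.1. The upper boundary for the number of DLTs among n participants is

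[ln((1−β)/α) − n·ln((1−p1)/(1−p0))] / [ln(p1/p0) − ln((1−p1)/(1−p0))]

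ln(0.9/0.1) = 2.1972, ln(0.3/0.1) = 1.0986 and ln(0.7/0.9) = −0.2513. The boundary is therefore (2.1972 + 0.2513n)/1.3499 = 1.628 + 0.1862n.

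| n | Boundary | DLTs needed | Written in 8.2? |
|---|---|---|---|
| 2 | 2.00 | 2 | yes |
| 6 | 2.74 | 3 | yes |
| 7 | 2.93 | 3 | no |
| 8 | 3.12 | 4 | no |

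The two written thresholds agree with the stated inputs. The line continues without any new assumption.

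**3. Chance of stopping under the written rule.** An arm stops if it has three or more DLTs in six, or if the first two participants both have DLTs and the next four have none.

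- At p = 0.3: 0.25569 + 0.09 × 0.7⁴ = 0.25569 + 0.02161 = 0.2773.
- At p = 0.1: 0.01585 + 0.01 × 0.9⁴ = 0.01585 + 0.00656 = 0.0224.

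**4. Adding the n=7 boundary.** Participant 7 matters only when the arm is still open with exactly two DLTs among six. Of the 15 possible placements of two DLTs among six, one (both in the first two) has already stopped the arm, which leaves 14.

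- At p = 0.3: 14 × 0.3² × 0.7⁴ = 0.3025. Multiplied by 0.3, this adds 0.0908. Total 0.2773 + 0.0908 = 0.3681.
- At p = 0.1: 14 × 0.1² × 0.9⁴ = 0.0919. Multiplied by 0.1, this adds 0.0092. Total 0.0224 + 0.0092 = 0.0316.

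**5. Adding the n=8 boundary.** An arm still open after seven has at most two DLTs, so it has at most three after eight. The boundary of four cannot be reached, and the probabilities stay at 0.368 and 0.032. If someone instead read three DLTs as sufficient at n=8 as well, they would be 0.459 and 0.043. The missing text therefore leaves room for readings between 27.7% and 45.9% at a 30% rate.

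**6. The ceiling.** 12/0.9 = 13.3, rounded up to 14. Per arm, 6/0.9 = 6.7, rounded up to 7, again 14 in total. Fifteen results from a loss above 1 − 12/14 = 14.3% and up to 1 − 12/15 = 20%. With independent 10% losses, the chance of at least 12 evaluable participants is 0.842 at 14 and 0.944 at 15.

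**The case against.** **Replacement might keep the number at risk to six.** Section 5.9.1 replaces only participants who had no study drug or procedure, and they cannot have a DLT. If all extra accrual were of that kind, six at risk per arm would hold. But the allowance behind the 15 is for unevaluable participants as well as drop-outs, and evaluability in Section 8.2 also requires adequate endpoint measurements. Treated but unevaluable participants are therefore among those the margin covers, and Section 8.2 does not limit the rule to six at risk.

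**There is other oversight.** This stands. A reader might infer that up to three of 15 participants would be unprotected. The documents do not support that. The monitoring committee reviews all adverse events and meets monthly (Sections 10.7 and 10.8), and Section 5.10 allows termination for the incidence or severity of adverse reactions. What is missing is the numerical rule. Three is also the worst case, in which all 15 are enrolled and treated.

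**The rule only closes accrual.** This also stands. A reader might take the rise from 27.7% to 36.8% as a reduction in exposure. In an arm of seven, a boundary at n=7 closes nothing. In an arm of eight, it spares one enrolment.

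**Fifteen is an estimate and a maximum.** A reader might infer a sample-size error, or a hidden 20% loss assumption. Neither follows. The figure is one above 14, a 15% loss (12/0.85 = 14.1) also rounds up to it, and the power statement uses six per arm whichever ceiling is meant. Nor is the odd total a defect: 1:1 is an allocation ratio, and an 8/7 split does no harm in a trial that disclaims definitive comparison between arms.

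**Conclusion.** The point holds as a gap between the accrual ceiling and the stopping rule. The plan permits seven or eight participants in an arm, defines the rule only to six, and leaves the denominator open. On its own SPRT inputs, three DLTs in seven cross the boundary, and the written rule does not act on them.

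The effect is on the toxicity conclusion. The chance of deeming an arm too toxic is 9.1 percentage points higher at a true DLT rate of 30% (27.7% to 36.8%) and 0.9 points higher at 10% (2.2% to 3.2%). This assumes independent DLTs at a constant rate, seven treated participants in the arm, and a three-of-six rule that acts as soon as the third DLT occurs. The n=8 boundary contributes nothing.

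The mismatch between 10% and 15 is a labelling matter and carries little weight by itself.

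**What to change.** In Section 8.2:

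1. State that the rule counts treated participants, whether or not they are evaluable for the immune endpoint. Say in the same clause which study treatment makes a participant count, since Section 7.2.10 ties a DLT to pembrolizumab.
2. Reconcile the rule with the ceiling by continuing the plan's own SPRT line beyond six: three DLTs at n=7. The boundary of four at n=8 can be listed for completeness, but it changes no stopping probability.
3. Either give the maximum as 14, changing the Trial Summary to match, or keep 15 and describe it as a ceiling with a margin above the 10% allowance (15 fits a loss of about 15% to 20%).

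This takes a few sentences and no extra participants. The statistical cost is the added false stopping, 3.2% in place of 2.2% at a 10% DLT rate.

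### Do the within-arm detectable differences of 0.39 and 0.58 in section 8.2 rest on the wrong standard deviation?

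*Combined protocol and SAP*

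**What the plan says.** Section 8.2 sets a target of 12 participants, "which was chosen as a feasible number that could be accrued within a 2 year accrual period", randomised 1:1. Its stated purpose for the immune endpoint is to "estimate the difference in the TILs at baseline and 3 weeks within each arm", and it disclaims definitive comparison between arms.

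The planning figures come from one external study, which put the difference in mean ratio "for patients treated with HIFU versus no HIFU to be 0.57, with standard deviations ranging from 0.27 to 0.40". The section assumes that the patients in that study who had no HIFU "are comparable to baseline measurements in our study", and says of the source: "These data provide an indication of the magnitude that could be detected in this study at baseline and 3 weeks". It calls the data a guideline.

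For n = 6 it then states that "we have 80% power to detect an effect size of 1.44 for the within-arm change in ratio of CD4" and CD8 cells, and that, depending on how variable the data are, "this is equivalent to detecting differences of 0.39 and 0.58, for assumed standard deviations of 0.27 and 0.40, respectively".

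No test, significance level or sidedness is given for this calculation; the 10% error rates in the same section belong to the DLT stopping rule. No SD of within-patient change and no baseline to 3-week correlation appears anywhere in the documents. The analysis paragraph of section 8.2 says that change in the proportion of CD8+ to CD4+ "tumor infiltrating lymphocytes (TILs) in the primary ablation zone will be estimated by arm".

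**The concern.** A standardised effect for a paired change is expressed in units of the SD of the change. To turn it into ratio units it must be multiplied by that SD. Section 8.2 multiplies it by SDs whose only stated source is a comparison of two groups of patients. Taking the no-HIFU group as a stand-in for baseline supplies a baseline level and spread. It says nothing about how strongly a patient's 3-week value follows the baseline value, and that correlation determines the SD of change.

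The two raw differences are the plan's only statement, in units of the endpoint, of what the within-arm comparison could detect. If the correlation were low, the true detectable change would be larger than printed, and power for the external difference of 0.57 could fall well below 80%. Section 8.1 also expects the trial to inform a larger one, so a reader might carry the figures forward.

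**Working it through.** **Inputs from section 8.2.** n = 6 per arm; power 80%; effect size 1.44; SDs 0.27 and 0.40; external difference 0.57. **Assumed, because not stated:** paired t-test, two-sided 5%. The correlation rho is not in the documents, so a range is shown.

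**1. The effect size reproduces.** With 5 degrees of freedom, critical t = 2.571 and noncentrality 1.44 × √6, power is 80.3%. Exactly 80% needs an effect of 1.4345.

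**2. The raw differences reproduce.** 1.44 × 0.27 = 0.389 and 1.44 × 0.40 = 0.576, printed as 0.39 and 0.58. The quoted SDs were therefore used directly as SDs of change.

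**3. What that implies if the SD is the same at both times.** SD of change = SD × √(2(1 − rho)). This equals the SD at rho = 0.5. The detectable change is 1.44 × SD of change.

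| rho | √(2(1 − rho)) | Detectable, SD 0.27 | Detectable, SD 0.40 | Power at 1.44 × quoted SD |
|---|---|---|---|---|
| 0 | 1.414 | 0.55 | 0.81 | 52% |
| 0.25 | 1.225 | 0.48 | 0.71 | 64% |
| 0.5 | 1.000 | 0.39 | 0.58 | 80% |
| 0.75 | 0.707 | 0.27 | 0.41 | 97% |

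Power is below 80% for rho under about 0.5 and above 80% for rho over it, so the printed figures may be optimistic or pessimistic.

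**4. What it implies with one SD per time point.** The SDs are quoted as a range from a two-group comparison, and one of those groups stands in for baseline, so this reading is just as open. SD of change = √(0.27² + 0.40² − 2 × rho × 0.27 × 0.40) = √(0.2329 − 0.216 × rho).

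| rho | SD of change | Detectable change |
|---|---|---|
| 0 | 0.483 | 0.69 |
| 0.25 | 0.423 | 0.61 |
| 0.5 | 0.353 | 0.51 |
| 0.75 | 0.266 | 0.38 |

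The SD of change equals 0.40 at rho = 0.0729 / 0.216 = 0.34, and 0.27 at rho = 0.16 / 0.216 = 0.74. The printed 0.58 and 0.39 then correspond to those two correlations.

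**5. Against the external difference of 0.57.** For 80% power the SD of change must be at most 0.57 / 1.4345 = 0.397.

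- Equal SDs of 0.27: power is 83% at rho = 0 and higher for any larger rho.
- Equal SDs of 0.40: power is 51%, 63%, 79% and 97% at rho 0, 0.25, 0.5 and 0.75. It reaches 80% at rho = 1 − 0.397² / (2 × 0.40²) = 0.51.
- One SD per time point: power is 64%, 75%, 88% and 98%. It reaches 80% at rho = (0.2329 − 0.397²) / 0.216 = 0.35.

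**The case for a change.** The strongest argument for a correction is that the sponsor chose to print a power statement and should print one that a reader can check. The text never says that 0.27 and 0.40 are meant as SDs of change, and its only source for them is a between-group comparison. The test and significance level must be guessed. A one-sided 5% two-sample normal approximation with 6 per group gives (1.645 + 0.842) × √(2/6) = 1.436, which also rounds to 1.44, and on that reading a group SD would be the right unit. The text says within-arm, however, and the exact two-sample t version gives 1.544, so the paired reading fits better. The power sentence also names the ratio with CD4 first, while section 3.1 and the analysis paragraph use CD8+ to CD4+. If the source figures are for CD4+/CD8+, their SDs do not carry over to the inverse.

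All of that stands as missing detail. It does not show that the figures are wrong. The sentence concerns the within-arm change and is conditional on assumed SDs, so a statistician can read those as SDs of change, and then 0.39 and 0.58 are exact. Nor can it be said that the SDs overstate sensitivity: under equal SDs every correlation above 0.5 gives more than 80% power. The order of the ratio cannot be settled from the documents.

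The argument from a later trial carries little weight. Estimating the change by arm will yield the SD of within-patient change in these patients. With about 6 per arm that estimate will be imprecise, but it is the relevant quantity, and a designer would start there rather than from the planning figure.

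**Conclusion.** No change to the plan is needed. The standardised effect of 1.44 is correct for a paired t-test with n = 6 at an assumed two-sided 5%, and the multiplication to 0.39 and 0.58 is correct. What is missing is a clause saying that 0.27 and 0.40 are taken as SDs of change, together with the test and significance level.

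The size of the uncertainty depends on a correlation that the documents do not give. Over rho from 0 to 0.75, the detectable change runs from 0.55 down to 0.27 for SD 0.27 and from 0.81 down to 0.41 for SD 0.40 under equal SDs, or from 0.69 down to 0.38 with one SD per time point. The printed 0.39 and 0.58 fall within the corresponding equal-SD ranges.

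Filling the gap would alter nothing in the trial. The number of participants was fixed by what could be accrued in two years, the within-arm analysis is estimation, and no success criterion uses either figure. A reader who wants the sensitivity in endpoint units can multiply 1.44 by whatever SD of change seems plausible.

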#### **4.4 Rationale for Endpoints**

This study is designed primarily to test whether interfering with immune suppression by blocking the molecular interaction between the PD-1 receptor and its cognate ligand, PD-L1, increases the number and activation of TILs that are induced by the local ablative therapy.

The study is also designed to examine the safety of HIFU and pembrolizumab. HIFU therapy for breast lesions and breast cancer is generally well tolerated. Based on our experience at UVA (n=20) there has been no evidence of grade 4 toxicities in patients who received HIFU. Pembrolizumab has been studied in numerous clinical trials to date and was found to be well tolerated with no dose-limiting toxicities at the standard dose of 200 mg (see Investigator's Brochure). Our proposed study is the first study to combine HIFU and pembrolizumab in humans and safety is our secondary endpoint.

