## **10.7 Data Safety Monitoring Plan**

The University of Virginia Cancer Center Data and Safety Monitoring Committee (CC DSMC) will provide oversight of the conduct of this study. The CC DSMC will report to the UVA Protocol Review Committee (PRC).

The UVA CC DSMC will review the following:

- All adverse events
- Audit results
- Application of study designed stopping/decision rules
- Whether the study accrual pattern warrants continuation/action
- Protocol violations

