## **10.8 DSMC Monitoring Schedule**

The UVA CC DSMC will meet every month for aggregate review of data. Tracking reports of the meetings are available to the PI for review. Issues of immediate concern by the DSMC are brought to the attention of the sponsor (and if appropriate to the PRC and IRB) and a formal response from the sponsor is requested. Per the UVA Cancer Center NIH approved institutional plan, this study will be audited approximately every 6 months.

**Product:** Pembrolizumab

**Protocol/Amendment No.:** UVA Breast 48

V04-13-21

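### The 10% error rates cited for the DLT stopping rule belong to an open-ended SPRT; cut off at 6 per arm, the rule closes an arm with a 30% DLT rate only 27.7% of the time

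*Combined protocol and SAP*

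**What the plan says.** Section 8.2 (Statistical Analysis Plan) gives the rule for each arm: "If the first two participants within an arm or 3 out of the 6 participants within an arm experience a DLT", the arm is judged too toxic and accrual to it stops. It derives the rule from Wald's SPRT, assuming "lower and upper DLT proportions of 0.1 and 0.3, respectively, and type I and II error rates of 10" percent. The target is 12 participants, 6 per arm, but "maximum target accrual is estimated at 15 participants", so under 1:1 allocation one arm could reach 8 and the other 7.

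Other safeguards are described. In Section 8.2, "Adverse events and DLTs will be summarized by frequency and magnitude for each arm and overall". Section 10.7 has the monitoring committee (DSMC) review all adverse events and the "Application of study designed stopping/decision rules". Section 10.8 adds "The UVA CC DSMC will meet every month for aggregate review of data". Section 5.10 allows early termination for a potential health hazard.

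No section gives the probability that the rule closes an arm at any true DLT rate.

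**The concern.** The 10% rates are the only error rates printed for this rule. A reader would naturally take them to mean that an arm with a 30% DLT rate is caught about nine times in ten. But an SPRT has its nominal error rates only when sampling continues until a boundary is crossed. Ending it after 6 participants changes both rates.

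This matters because Section 4.4 states "Our proposed study is the first study to combine HIFU and pembrolizumab in humans", and this is the only numeric rule for closing an arm. Section 8.2 openly says that power to compare arms is limited, but it gives no matching caution for the safety rule. Someone who believes the type II error is 10% would read an arm that stays open as good evidence of tolerability.

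**Working it through.** **Inputs, all from Section 8.2:** p0 = 0.1, p1 = 0.3, α = β = 0.10; close at 2 of the first 2 or 3 of 6; 6 per arm; at most 15 in total. The calculation assumes that each DLT is known before the next participant enters.

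**1. The plan's boundary reproduces.** In terms of the DLT count, the SPRT lines are ±intercept + slope × n:
- slope = ln(0.9/0.7) / ln(0.27/0.07) = 0.2513/1.350 = 0.1862
- intercept = ln(0.9/0.1) / 1.350 = 2.197/1.350 = 1.6277
- upper line: 2.000 at n=2, 2.745 at n=6, 2.931 at n=7, 3.117 at n=8
- lower line: −0.138 at n=8, 0.048 at n=9

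The upper line gives 2 of 2 and 3 of 6, as written. The lower line is below zero until n=9, so an arm of 6 can only close or end undecided.

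**2. The open-ended test.** Exact recursion without truncation gives error rates of 7.0% and 9.2%, consistent with the nominal 10%. The mean sample size is about 17 per arm at a 10% DLT rate and 14 at 30%.

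**3. The rule cut off at 6.** P(close) = P(X ≥ 3 of 6) + P(first two DLTs, then none in four).
- p = 0.1: 0.01585 + 0.01 × 0.9⁴ = 0.01585 + 0.00656 = 0.0224
- p = 0.3: 0.25569 + 0.09 × 0.7⁴ = 0.25569 + 0.02161 = 0.2773

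Non-closure is therefore 97.8% at a 10% DLT rate and 72.3% at 30%.

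**4. Other true rates, and arms that reach 8.**

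| True DLT rate | Closed within 6, as written | Arm of 8, SPRT line continued (3 of 7, 4 of 8) | Arm of 8, count of 3 kept |
|---|---|---|---|
| 10% | 2.2% | 3.2% | 4.3% |
| 20% | 11.5% | 16.1% | 21.4% |
| 30% | 27.7% | 36.8% | 45.9% |
| 40% | 47.6% | 59.3% | 69.2% |
| 50% | 67.2% | 78.1% | 85.9% |

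In an arm of 7 the two extensions agree, because both require 3 DLTs. They part only at an 8th participant.

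**5. Can any boundary at this size reach 10%/10%?** The smallest fixed-sample test with both errors at or below 10% needs 25 per arm (close at 5 or more DLTs; errors 9.8% and 9.0%). No boundary within 6 or 8 participants can do it.

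**6. What an open arm tells the reader.** The likelihood ratio for 30% against 10%, given only that the arm stayed open, is 0.7227/0.9776 = 0.74, which is weak evidence. The count says more. With k DLTs in 6 the ratio is 3^k × (7/9)^(6−k): 0.22 for k=0, 0.85 for k=1 and 3.29 for k=2. Two DLTs in 6 favour the 30% rate, yet leave the arm open unless both were in the first two participants.

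**The case against.** The strongest reply is that the plan claims no achieved error rates. It presents the 10% figures as assumptions from which the boundary was derived, and the boundary is correctly derived. That stands: nothing in the boundary is miscalculated. But no other error rates are given and the truncation is not mentioned, so the text invites the wrong reading.

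A second reply is about terms. In an SPRT, a type II error means crossing the lower line, which cannot happen within 6, so 72.3% is strictly a probability of no decision. This also stands as terminology. Under either name, an arm with a 30% DLT rate stays open 72.3% of the time.

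Third, 27.7% includes paths where the deciding DLT is in the sixth participant, when an arm of 6 is already full. Crossing by the fifth participant has probability 0.16308 + 0.09 × 0.7³ = 19.4% at a 30% rate. Section 7.2.10 also sets no DLT observation window, so the assumption that each DLT is known before the next entry may fail. Both points make the protection weaker than 27.7% suggests.

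Finally, this is a small pilot sized on feasibility, with monthly DSMC review and a general termination clause. These safeguards limit the consequence and are a good reason to leave the boundary alone. They do not tell the reader how sensitive the rule is. The question about a 7th or 8th participant is a smaller clarification, arising only if accrual goes past 12.

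**Conclusion.** The concern holds. The boundary matches its SPRT inputs, but the 10% error rates do not describe the rule as applied to 6 participants per arm. At a 10% DLT rate the arm closes 2.2% of the time, which is better than the nominal 10%. At a 30% DLT rate it closes 27.7% of the time, leaving 72.3% unclosed against a nominal 10%. Even the more generous extension to 8 participants reaches only 45.9%.

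The figures are exact for the rule as written. They assume independent DLTs at a constant rate within an arm, each known before the next enrolment. This should be corrected in the text; it is not a reason to redesign the study.

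**What to change.** In Section 8.2:

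1. Keep the SPRT inputs so that the boundary can be reproduced, but say that the 10% rates apply only to the untruncated test.
2. Give the exact closure probabilities at 6 per arm as the rule's operating characteristics: 2.2%, 11.5%, 27.7%, 47.6% and 67.2% at true DLT rates of 10%, 20%, 30%, 40% and 50%. Note the assumption that each DLT is known before the next enrolment.
3. State that the rule has no boundary for declaring an arm acceptable within 6 participants, so an arm that stays open is undecided.
4. State what count applies to a 7th or 8th participant in an arm, and give the matching column of closure probabilities.

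The cost is some SAP wording and one small table. No participants or procedures are added and the boundary can stay as it is. The price is that the plan will show a much lower sensitivity than the 10% figure implies. Whether that protection is acceptable is for the sponsor and the DSMC to decide.
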